**PROTOCOL SYNOPSIS**

Protocol Title:	A PHASE II TRIAL OF ADJUVANT PROSTVAC-V/F IN SUBJECTS AT HIGH RISK FOR RELAPSE AFTER RADICAL PROSTATECTOMY
Site Numbers & Names:	1. Hollings Cancer Center, Medical University of South Carolina, Charleston, SC 2. Ralph Johnson VA Medical Center, Charleston, SC
Research Hypothesis:	The hypothesis is that, in patients at high risk for relapse of PCa after radical prostatectomy, treatment with the PROSTVAC-V/F vaccine will improve Relapse Free Survival (RFS) compared with that expected for similar subjects given no adjuvant therapy.
Study Schema:	PROSTVAC-V $2 \times 10^8$ pfu subQ x 1, followed by PROSTVAC-F $1 \times 10^9$ pfu subQ x 6
Study Objectives:	
 
1. The primary endpoint is to determine the probability of RFS at 2 years after prostatectomy, and to compare it to RFS probability for historical control subjects without adjuvant treatment.
 
2. Secondary objectives are as follows:           
 
a) Compare observed RFSs to the predicted RFS values for the subjects as if they had received no adjuvant therapy. The predicted ("virtual") RFS for each subject will be calculated by standard algorithms.
 
b) Relate serial measurement of immunologic parameters, SNPs to RFS
 
c) Describe the toxicity for the treatment in this patient population
 
 
 

Study Design:	The study will be a Phase II, open-label trial conducted at two centers in the United States.
Accrual Goal:	30 evaluable subjects out of 33 total enrollees
Accrual Rate: (Number of subjects expected per month)	1.85 subjects per month x 18 months = 33 subjects. Assuming an in-evaluability rate of about 10%, this will give us 30 evaluable subjects.
Correlative Studies:	
 
1. Lymphocyte, monocytes subsets
 
2. Immunoglobulin, FcR SNPs
 
3. Plasma IL6, IL10, VEGF
 
4. Exon sequencing on tumor from FFPE tissue
 

Optional Study :	Potential patients will be approached to participate in an optional sub-study looking at sociobiological responses to stress in prostate cancer survivors.

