Statistics for Main Study:	
Statistical considerations:
 
Primary Objective: The primary endpoint will be a binary indicator of relapse status at the 2 year follow-up visit. Enrollment and treatment initiation must take place no more than 120 days after prostatectomy. Two-year RFS will be estimated as a proportion with an exact 95% confidence interval. RFS will also be treated as a time-to-event variable and Kaplan-Meier curves will be created; median and 95% confidence intervals will be reported.
 
The data from this trial will be compared with results from historical control data obtained from a multi-institutional database which includes high-risk, post-prostatectomy subjects without adjuvant therapy (n = 243), and from a published clinical trial (n = 98). The estimated 2-year probability of RFS of high-risk subjects after prostatectomy is 0.6. We define an "interesting" improvement in RFS to be 30% (i.e. increase in the probability of RFS from 0.6 to 0.78). Assuming a one-sided alpha = 0.1, with 30 patients in a group, we have 80% power to detect this difference based on an exact binomial test. Thus if among 30 evaluable subjects, at least 24 are recurrence free at 24 months, we will reject the null hypothesis (2-year RFS=0.60) and conclude that the PROSTVAC intervention improves RFS relative to the RFS of similar patients receiving no adjuvant therapy.
 
Secondary objectives: a) A secondary objective will be a comparison of observed RFS times with the predicted RFS times for the treatment cohort using the Duke and CaPSURE nomograms. The comparison will be performed using the logrank test of the observed and predicted RFSs.
 
b) Biochemical and genomic measurements will be graphically displayed to evaluate their distributions. Transformations will be taken as appropriate. Cox regression will be used to estimate hazard ratios measuring the association between these measures and RFS. 95% confidence will be estimated for the hazard ratios as appropriate.
 
c) Toxicities will be tabulated by CTCAE grade and type.

-----------------------------------	--

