#### **2.2.2 Adjuvant Radiation, Chemotherapy, or Androgen Deprivation Therapy For High Risk PCa**

Systemic adjuvant therapy, using cytotoxic agents or hormone manipulation, has been shown to improve overall survival following surgery for subjects with clinical localized cancers of the breast, lung, colon, and other sites. However, adjuvant therapy for subjects treated with radical prostatectomy for PCa has not been widely studied or consistently applied. While traditional local therapies provide adequate control for the vast majority of PCa patients, a substantial minority of patients relapses and is at risk for a fatal outcome. Adjuvant therapy for subjects treated with radical prostatectomy for PCa has not been widely studied or consistently applied.

Post-prostatectomy adjuvant therapy for PCa has largely consisted of radiation therapy or ADT. Recent large, prospective, randomized studies demonstrate that external beam radiation to the prostatic fossa can delay biochemical failure, and improve disease-specific survival in subsets of patients with T3a disease, especially those subjects with positive surgical margins (3,4). However, studies are inconsistent as to whether radiation clearly improves outcomes for more advanced cases (pT3b or pN1). In addition radiation can cause significant side effects such as bowel toxicity, increased frequency of strictures, and possibly, secondary malignancies.

Few data exist on the role of adjuvant chemotherapy for patients at high risk of relapse after prostatectomy. The initial studies failed to show clear benefit, however, due to the lack of active agents (5-7). In the past decade the taxanes have been identified as cytotoxic agents with significant anti-tumor activity in PCa (8,9). Attempts have been made to develop chemotherapy regimens with adjuvant activity against PCa. Three large-scale, phase III studies of adjuvant

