chemotherapy have been launched, but have been difficult to complete. The SWOG 9921 study compared adjuvant ADT with ADT plus six cycles of mitoxantrone. The study was terminated short of the planned accrual due to an excess of acute leukemia cases in the chemotherapy arm (10). TAX3501 was a multicenter trial comparing ADT with ADT plus six cycles of docetaxel. This study too was terminated after only a small proportion of the total enrollment was accrued. The Veterans Affairs Cooperative Studies Program is sponsoring CSP553, a randomized study comparing prostatectomy versus prostatectomy plus docetaxel for patients with high-risk, localized PCa. Accrual has been completed, but no report has been published. One phase II trial of adjuvant weekly single-agent docetaxel has been presented (11). In this trial 77 post-prostatectomy subjects at high risk for relapse or disease progression were treated. Compared with the predicted PFS for the patients if they had not received adjuvant chemotherapy, there was little or no improvement in PFS from chemotherapy.

The results from studies of adjuvant ADT are also variable. The only randomized, prospective study of adjuvant ADT was the E3886 trial reported by Messing, et al. (12,13). This study demonstrated that ADT given immediately after prostatectomy (rather than waiting for clinical relapse) improves progression-free, disease-specific, and overall survival in PCa patients with positive lymph nodes. Older analyses of adjuvant ADT for other subgroups are ambiguous (14). Recent prospective (15) and retrospective (16) analyses are consistent with a beneficial effect from adjuvant ADT in a wide spectrum of high-risk patients, possibly better than would be expected from observation alone. However, ADT is associated with significant side effects. These include increased body fat, insulin resistance, loss of libido, increased cardiac events, and potentially delay in or prevention of recovery of sexual function after prostatectomy. Furthermore, it is not clear that adjuvant ADT "cures" PCa patients. Progression-free survival curves from the E3886 trial show continuing relapses over time, without a clear plateau or "break" in the downward slope of group survival curves, such as would be seen with a curative treatment.

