## **10 STATISTICAL CONSIDERATIONS**

We will compare RFS at two years for the patients treated with PROSTVAC to that of untreated historical controls. A secondary efficacy objective will be a comparison of the observed RFSs for the treated subjects with the calculated RFSs for the same subjects as if they had not received adjuvant therapy .

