We define an “interesting” reduction in the risk of relapse to be 30% (i.e., increase in the probability of RFS from 0.6 to 0.78). Assuming a one-sided alpha = 0.1, with 30 evaluable patients, we have 80% power to detect this difference based on an exact binomial test. Thus if among 30 evaluable subjects, at least 24 are recurrence free at 24 months, we will reject the null hypothesis (2 year RFS=0.60) and conclude that the PROSTVAC intervention improves RFS relative to the current standard of care in this patient population (one-sided p-value  $\leq 0.025$ ). Anticipating a final sample size of 30 patients with 10% drop out rate, we plan to enroll 33 patients for this study.

**Interim Analysis:** An interim analysis for futility will be performed through Simon’s minimax two-stage design (Simon, 1989) when a total number of 19 patients are evaluable. The design is described as follows:

**Stopping criteria:** Stop the study if there are 11 or fewer recurrence free among the first 19 evaluable patients. Otherwise, additional patients will be accrued resulting in a total evaluable sample size of 30.

**Decision rule at N=30 evaluable patients:** Reject the null hypothesis if there are 22 or more recurrence free among the 30 evaluable patients. We claim that the PROSTVAC intervention improves RFS relative to the current standard of care in this patient population. This design controls the type I error rate at 0.1 and yields the power of 0.8.

**Safety Monitoring:** Continuous safety monitoring will be performed with early stopping rules in the case of unacceptable risk to the subjects, defined as evidence in favor of a risk of a grade 3 or greater toxicity deemed to be possibly related to treated of 25% vs. an acceptable rate of 10%. Stopping criteria are shown in the table below. The stopping rules are based on a likelihood ratio. Specifically, the likelihood ratio is calculated based on a hypothesized 10% event rate (safe) vs, a 25% event rate (unsafe) and likelihood ratios in excess of 8 (in favor of an event rate of 25%)

are considered sufficient evidence to stop the trial. For example, 7 events in 33 patients yields an event rate of 0.21, which has a likelihood ratio of 9.21 favoring a rate of 25% vs. 10%.

Stop if:	Likelihood Ratio	Observed Event Rate
3 events in $\leq 6$ patients	$\geq 9.04$	$\geq 0.50$
4 events in $\leq 12$ patients	$\geq 9.08$	$\geq 0.33$
5 events in $\leq 18$ patients	$\geq 9.13$	$\geq 0.28$

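### Section 10.1 words the primary conclusion against an undefined standard of care, but the 0.60 benchmark supports only a claim against no adjuvant therapy

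*Combined protocol and SAP*

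**What the plan says.** Section 10.1 gives the conclusion twice. Under Sample Size Justification, with at least 24 of 30 men recurrence free, the investigators will "conclude that the PROSTVAC intervention improves RFS relative to the current standard of care in this patient population". Under the two-stage decision rule, with 22 or more of 30, the text reads: "We claim that the PROSTVAC intervention improves RFS relative to the current standard of care in this patient population".

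Elsewhere the comparator is different:

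- The synopsis hypothesis expects an improvement "compared with that expected for similar subjects given no adjuvant therapy".
- The synopsis, for the same test, will "conclude that the PROSTVAC intervention improves RFS relative to the RFS of similar patients receiving no adjuvant therapy".
- Section 10 opens: "We will compare RFS at two years for the patients treated with PROSTVAC to that of untreated historical controls".
- Section 10.2.1 describes the predicted RFS values as those expected without adjuvant treatment.

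The null value of 0.60 comes from two sources in Section 10.1. In the database of 243 men, no one had adjuvant therapy, and 2-year RFS was 0.645. The E3886 trial is quoted with n = 98 and 2-year RFS 0.56, without saying which arm or arms that figure describes.

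**The concern.** The sentence that follows rejection fixes in advance what a positive trial means. Observation and standard care need not be the same for every man enrolled. Section 2.2.2 reports that radiation delays biochemical failure and improves disease-specific survival in subsets with T3a disease, "especially those subjects with positive surgical margins". It reports that immediate ADT "improves progression-free, disease-specific, and overall survival in PCa patients with positive lymph nodes". Section 4.3 admits men with positive margins and men with pN1 disease. Its note admits men with pT3a disease and no other qualifying feature only if they decline adjuvant radiation, so the protocol itself treats radiation as an available choice for them.

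If standard of care includes those options, rejecting 0.60 does not show superiority to it, and the stated type I error of 0.1 does not describe the risk of a false claim.

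**Working it through.** **Inputs (Section 10.1).** Null 0.60, alternative 0.78, one-sided alpha 0.1, 30 evaluable men. Two-stage rule: stop if 11 or fewer of the first 19 are recurrence free; otherwise continue to 30 and reject at 22 or more. A single-stage cutoff of 24 of 30 is also stated.

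**1. Reproduce the plan's error rates.** For a true 2-year RFS of p, the probability of passing the two-stage rule is

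P(pass) = Σ (x = 12 to 19) C(19, x) p^x (1 − p)^(19 − x) × P[Bin(11, p) ≥ max(0, 22 − x)].

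- p = 0.60 gives 0.0934.
- p = 0.78 gives 0.8007.

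These match the stated 0.1 and 0.8. As a test of 0.60, the two-stage rule does what the plan says. The 24/30 cutoff gives P[Bin(30, 0.60) ≥ 24] = 0.0172 and power 0.4992, so it does not match the stated 80%. That conflict between cutoffs is a separate matter.

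**2. Apply the rule to the wider claim.** The claim of beating standard care is false when the vaccine's 2-year RFS only equals that of standard care. The documents give no 2-year RFS for standard care, so the values below are assumed.

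| Assumed standard-care 2-year RFS | Pass 11/19, 22/30 | Pass 24/30 |
|---|---|---|
| 0.60 (plan's null) | 0.093 | 0.017 |
| 0.65 | 0.223 | 0.059 |
| 0.70 | 0.430 | 0.160 |
| 0.75 | 0.672 | 0.348 |
| 0.80 | 0.870 | 0.607 |

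Error control at 0.1 holds for the wider claim only if standard-care RFS is close to 0.60, which is the case where standard care amounts to observation.

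**3. Does 0.60 already include adjuvant-treated men?** The larger source does not. For E3886, Appendix B gives 5-year progression-free survival of 83% with immediate ADT (47 men) and 27% with deferred ADT (51 men). Assuming exponential curves, S(2) = S(5)^0.4:

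- Deferred arm: 0.27^0.4 = 0.592.
- Immediate arm: 0.83^0.4 = 0.928.
- Pooled: (47 × 0.928 + 51 × 0.592)/98 = 0.753.

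The quoted 0.56 fits the deferred arm better. Pooling is not strictly excluded: a curve cannot rise, so the pooled 2-year value need only be at least (47 × 0.83 + 51 × 0.27)/98 = 0.539. The arm should be stated. Even so, Section 10.1 nowhere presents 0.60 as the outcome under adjuvant treatment.

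**The case against.** The strongest reply is that the phrase is loose, not false. Section 2.2.2 says adjuvant treatment after prostatectomy is little studied and unevenly used, that radiation results conflict for pT3b and pN1 disease, and that ADT results vary and carry important side effects. On that account standard of care could mean observation. Section 4.4 also excludes any neoadjuvant or adjuvant therapy, so every man enrolled goes without it and a no-adjuvant benchmark is the natural one. The comparator is clear in several other places, and the sentence itself states the null as 0.60.

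Most of this stands. It shows that the benchmark suits the hypothesis and that a careful reader can recover the intended meaning. It does not justify the phrase: the term is undefined, and the same section reports benefit from adjuvant options in eligible groups. If observation is meant, the synopsis already says so exactly.

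A reader might go further and infer from Appendix B that the trial could be declared positive with a result worse than immediate ADT, since 22/30 is 73% and that arm had 83% at 5 years. The documents do not support that as a measure of the problem:

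- The 83% comes from 47 node-positive men, whereas pN1 is one of six listed qualifying features, plus the pT3a route. Nothing suggests that pN1 will predominate.
- Relapse is defined differently. Section 10.1 gives PSA above 0.1 ng/mL for E3886. This trial uses a confirmed value of 0.2 ng/mL or more after all doses, and counts new therapy as an event.
- In the immediate-ADT arm 8 of 47 men (17%) had detectable postoperative PSA. This trial requires a value below 0.2 ng/mL.
- The first of the two sentences carries the 24/30 cutoff, which is 80%. The exact 95% intervals for 22/30 (54.1% to 87.7%) and 24/30 (61.4% to 92.3%) both contain 83%.

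**Conclusion.** The inconsistency is real and minor. Two sentences in Section 10.1 state a broader conclusion than the hypothesis, the synopsis rule, the opening of Section 10 and the larger benchmark source allow. The 0.093 type I error and 0.801 power of the two-stage rule apply to a claim against no adjuvant therapy, taking 0.60 as the right value for such men. They do not apply to a claim against standard care unless standard care is observation. The 0.22 to 0.87 range for a false claim under the two-stage rule rests wholly on assumed standard-care values of 0.65 to 0.80 and shows direction only.

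It would be too strong to say that standard care in this population is known to be adjuvant treatment, or that the design or null is wrong. The documents establish neither.

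**What to change.** In both sentences of Section 10.1, replace the reference to standard of care with the synopsis comparator, so that each says the intervention "improves RFS relative to the RFS of similar patients receiving no adjuvant therapy". Add one sentence stating that no conclusion is drawn against adjuvant radiation or ADT.

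The cost is two edited sentences and one new one. The null, the sample size and the cutoffs are not changed by this fix. The downside is a narrower claim.

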## 4 INVESTIGATIONAL PLAN

### 4.1 STUDY DESIGN AND DURATION

This will be a Phase II study of adjuvant PROSTVAC-V/F in subjects at high risk for relapse after radical prostatectomy. The study will be carried out at MUSC and the VAMC. The coordinating center will be at the Sponsor-Investigator Support Unit. Additional sites may be recruited as needed to ensure accrual.

We anticipate a two year period of accrual and an equal period of follow up for each subjects, or approximately four years total, from the point of completions of approvals and contracts.

The study population will be post-prostatectomy patients whose pathology reports documents one or more high risk features, including one or more of the following: pT3b or pT4, pN1, pT3a (without adjuvant radiation), positive margins, pre-operative PSA  $\geq 10$  ng/mL, Gleason score 8-10. Each site PI will be responsible for reviewing all prostatectomy cases to determine the patient's eligibility and interest in participating in the study.

Forty evaluable subjects (total 44 subjects) will be enrolled. Subjects will be treated with PROSTVAC-V/F alone. Subjects will be followed for relapse for two years after prostatectomy.

Prior to any study specific activities, the patient must be aware of the nature of his/her disease and willingly consent to the study after being informed of study procedures, the experimental therapy, possible alternatives, risks and potential benefits. IRB approval of this protocol and accompanying consent is required.

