### **10.1 STATISTICAL CONSIDERATIONS FOR THE PRIMARY OBJECTIVE**

**Endpoint:** The primary endpoint will be a binary indicator of relapse status at the 2 year follow-up visit after prostatectomy. Due to interval-censoring, using a time-to-event RFS outcome may lead us to anti-conservative estimates due to some patients having follow-up weeks to months after the 2 year anniversary of their surgery and recurrences defined at those later timepoints would not be captured in an estimate of 2 year RFS based on a Kaplan-Meier approach. A time-to-event analysis of RFS will also be performed, but not for making inferences for the primary objective. Patients who do not have data available for a two-year follow-up will be censored at the last visit at which they were known to be recurrence-free. Patients who drop out will be replaced for up to 4 patients. However, those who choose to discontinue treatment prior to a recurrence (or other event defined in [Section 4.6](#)) but wish to remain in the study, will be followed through 24 months to evaluate their disease status based on the intent-to-treat principle. These subjects will not be replaced.

**Analysis Plan:** The primary endpoint will be a binary indicator of relapse status at the 2 year follow-up visit after prostatectomy. Two-year RFS will be estimated as a proportion with an exact 95% confidence interval. RFS will also be treated as a time-to-event variable and Kaplan-Meier curves will be created and median and two year RFS will be reported with 95% confidence intervals.

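### The 19-man futility look depends on two-year outcomes that arrive at about months 30 to 36, after enrolment and dosing have ended, so it cannot gate stage 2 accrual as written

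*Combined protocol and SAP*

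**What the plan says.** Section 10.1 defines the endpoint: "The primary endpoint will be a binary indicator of relapse status at the 2 year follow-up visit after prostatectomy". Its Interim Analysis paragraph places a Simon minimax futility look "when a total number of 19 patients are evaluable". The stopping criterion is "Stop the study if there are 11 or fewer recurrence free among the first 19 evaluable patients", followed by "Otherwise, additional patients will be accrued resulting in a total evaluable sample size of 30". The final rule is "Reject the null hypothesis if there are 22 or more recurrence free among the 30 evaluable patients". The design values are given as "increase in the probability of RFS from 0.6 to 0.78", with type I error 0.1 and power 0.8.

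The Protocol Synopsis plans accrual as "1.85 subjects per month x 18 months = 33 subjects". Section 4.1 differs: "We anticipate a two year period of accrual and an equal period of follow up for each subjects, or approximately four years total", with 44 men enrolled for 40 evaluable. Section 10.4 counts a man as evaluable once he has received one dose of PROSTVAC-V. It sets no follow-up requirement. Treatment must start within 120 days of surgery (Section 5.1), and the last dose is on Day 141 (Section 5.2.1).

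**The concern.** A two-stage design limits enrolment only if the stage 1 result is known before stage 2 opens. Here each man's outcome takes two years from surgery, while the whole cohort is to be enrolled in 18 or 24 months. Section 10.1 words stage 2 accrual as conditional on the look, but no section pauses enrolment or gives a shorter-term endpoint for the look.

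An oversight committee reading Section 10.1 could expect that, if the vaccine does nothing, there is an even chance of enrolling only about 19 evaluable men. On the planned schedule all the men would already be enrolled and fully dosed when the rule is applied.

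**Working it through.** **Step 1. Reproduce the design.** Stage 1 has 19 men (stop if 11 or fewer successes), the total is 30 (reject if 22 or more), p0 = 0.60 and p1 = 0.78.

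- P(reject) = Σ over x = 12 to 19 of P(X₁ = x) × P(X₂ ≥ 22 − x), with X₁ ~ Bin(19, p) and X₂ ~ Bin(11, p). This gives 0.0934 at p = 0.60 and 0.8007 at p = 0.78, in line with the stated 0.1 and 0.8.
- An exhaustive minimax search for these rates returns the same bounds, 11/19 and 22/30.
- Early stopping under the null: P(X₁ ≤ 11) = 0.512. Expected evaluable men: 19 + (1 − 0.512) × 11 = 24.4.

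**Step 2. Date the look.** Inputs: 1.85 men per month and about 10% in-evaluable (Synopsis), and surgery 0 to 120 days (0 to 3.94 months) before enrolment. I assume uniform accrual and Day 1 at enrolment. One month is 30.4375 days.

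- 19th evaluable man enrolled: 19/1.85 = month 10.3, or (19/0.9)/1.85 = 21.1/1.85 = month 11.4 allowing for in-evaluable men.
- His two-year point: enrolment + (24 − 3.94) to enrolment + 24. Earliest 10.3 + 20.1, which is month 30.3 before rounding; latest 11.4 + 24 = month 35.4.
- A PSA that needs confirmation after 30 days adds about 1.0 month: month 36.4.

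**Step 3. Date the end of accrual and dosing.** Accrual ends at month 18. The last man's Day 141 dose is 140 days later: 18 + 4.6 = month 22.6.

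| Schedule | Look (with PSA confirmation) | Accrual ends | Last dose |
|---|---|---|---|
| 33 men, 18 months (Synopsis) | 30.3–35.4 (36.4) | 18 | 22.6 |
| 33 men over 24 months (10.1 size, 4.1 period) | 33.9–39.4 (40.3) | 24 | 28.6 |
| 44 men over 24 months (4.1) | 30.4–35.5 (36.5) | 24 | 28.6 |

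On the Synopsis schedule the look falls 12.3 to 18.4 months after accrual closes and 7.7 to 13.8 months after the last dose. In both other rows it also follows accrual and dosing.

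**Step 4. Could the rule act sooner?** Passing stage 1 needs 12 two-year successes. These cannot exist before 12/1.85 + 20.06 = month 26.5. The stop bound is 8 failures among 19, and failures can be seen early. In a simulation under the null (one-year RFS 0.751 as in the Section 10.1 database, two-year 0.60, piecewise exponential, relapse counted only after the last dose plus one month), 8 failures are known by month 18 with probability 0.06 to 0.17 for a surgery-to-enrolment lag of 0 to 120 days. By month 15 the probability is 0.01 to 0.05.

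**Step 5. Cost of a real gate.** The hold lasts from the 19th evaluable enrolment to his outcome, 20.1 to 24.0 months. Stage 2 needs 11/0.9/1.85 = 6.6 months. Total duration: 11.41 + 20.06 + 6.61 + 20.06 = 58.1 months, up to 11.41 + 24 + 6.61 + 24 = 66.0 months.

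**Step 6. Cost of dropping the gate.** Single stage, 30 men: rejecting at 22 or more gives alpha 0.0940 and power 0.8025. Rejecting at 24 or more, the bound also stated in the Synopsis and the Section 10.1 sample-size paragraph, gives alpha 0.017 and power 0.50.

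**The case against.** - **Evaluable may mean one dose.** Under Section 10.4, 19 men would be evaluable near month 10 and the gate could operate. The reading is open on the text, but it does not save the rule. The bound of 11/19 is calibrated to a two-year rate of 0.60. Applied at short follow-up, when more men are still recurrence free, it would not have the stated operating characteristics.
- **The schedule is a forecast.** Section 4.1 speaks of what is anticipated, and the conditional wording in Section 10.1 could imply an unstated hold. If so, the timeline is what needs correcting, by well over a year. Slower accrual would leave men still to enrol at the look only below roughly (33 − 21.1)/20 = 0.6 per month, about a third of the planned rate.
- **Early failures give some protection.** True, but the probability is small (step 4) and no rule for acting on them is written. A reader might infer that 33 men would be enrolled in every case; that is too absolute.
- **The purpose is inferred.** A reader might say that a promised safeguard for participants is missing. The plan calls the look a futility analysis and nowhere gives sparing men vaccination as its aim.
- **Follow-up after a stop.** A reader might infer that stopping would discard outcomes of men already treated. Section 10.1 does not say whether their follow-up would end, so this is unspecified.

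**Conclusion.** The point holds as an operational contradiction. On the planned schedule the futility rule cannot limit enrolment or vaccination, apart from the small chance of seeing 8 early failures. The 51% early-stop probability and the expected 24.4 evaluable men under the null would not become fewer men enrolled. This rests on uniform accrual at the planned rate and on reading the look as two-year status, the only reading under which 11/19 has its stated properties. It holds for 18-month or 24-month accrual and for 33 or 44 men.

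A reader might infer that the late look undermines the primary test. It does not: alpha is 0.0934 with the binding look and 0.0940 without it, and power is 0.80 either way. The plan should be changed because the rule and the schedule disagree, not because the inference is invalid.

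**What to change.** In Section 10.1, state that the 19 men must have two-year status or an earlier relapse. Reconcile this with the Synopsis accrual plan, Section 4.1 and Section 10.4 in one of two ways.

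- **(a) Drop the accrual condition.** Report the 19-man result to the DSMC as non-binding, follow every vaccinated man to two years, and use a single-stage test of 30 men with one rejection bound. At least 22/30 matches the stated 0.1 and 0.8; at least 24/30 does not (alpha 0.017, power 0.50). The plan states both, so the choice must be made explicitly.
- **(b) Keep the gate.** State the accrual hold of about 20 to 24 months and a total duration of about 58 to 66 months, in place of approximately four years.

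Option (a) costs protocol wording. The sponsor gives up a binding futility stop that on this schedule could at most save some late follow-up. Option (b) costs about 10 to 18 months beyond the 48 in Section 4.1 (58 − 48 and 66 − 48).
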